1.2 STUDY DESIGN

Study GO43104 is a Phase III, randomized, open-label, multicenter study of lurbinectedin in combination with atezolizumab compared with atezolizumab alone

administered as maintenance therapy in participants with ES-SCLC after first-line induction therapy with carboplatin, etoposide, and atezolizumab. Participants are required to have an ongoing response or SD per the Response Evaluation Criteria in Solid Tumor (RECIST) v1.1 after completion of 4 cycles of carboplatin, etoposide, and atezolizumab induction treatment in order to be considered for eligibility screening for the maintenance phase.

The study consists of 2 phases: an induction phase and a maintenance phase.

Participants who have been diagnosed with ES-SCLC and are treatment-naïve for their extensive-stage disease have to provide written informed consent prior to entering screening for the induction phase (induction screening). Participants who fulfill the eligibility criteria (see protocol Section 5.1 and 5.2) will be enrolled to receive 4 cycles of carboplatin, etoposide and atezolizumab induction treatment. The diagnosis of ES-SCLC will be based on the Veterans Administration Lung Study Group staging system (see protocol Appendix 17). Participants will receive 4 cycles of induction treatment unless they experience unacceptable toxicity or disease progression or they withdraw consent.

Participants must fulfill the eligibility criteria for the maintenance phase (see protocol Section 5.1.2 and 5.2.2) prior to randomization (maintenance screening). Participants who have received fewer than 4 or more cycles of carboplatin, etoposide and atezolizumab as induction, or experience progressive disease (PD) during the induction phase will not be eligible for the maintenance phase.

Following the induction therapy but before randomization, participants may receive prophylactic cranial irradiation (PCI) at the investigator's discretion per local standard. In accordance with National Comprehensive Cancer Network (NCCN) guidelines, magnetic resonance imaging (MRI) surveillance can be considered as an alternative option to PCI ([National Comprehensive Cancer Network 2021](#)).

[figure not shown]
Participants who receive consolidative thoracic radiation with curative intent or the intent to eliminate residual disease or participants with lesions that require palliative radiotherapy are not eligible for the maintenance phase of this study.

Randomization must occur within 5 weeks (35 days) from the day of the administration of the last dose of atezolizumab, carboplatin and/or etoposide (whichever occurs last). Participants receiving PCI must be randomized within 9 weeks (63 days) from the last dose of atezolizumab, carboplatin and/or etoposide (whichever occurs last).

In order not to confound the evaluation of overall survival (OS), crossover will not be allowed from Arm B (atezolizumab) to Arm A (atezolizumab in combination with lorbinecetin).

The study schema is shown in Figure 1.

Figure 1 Study Schema

1L=first-line; CNS=central nervous system; ECOG PS=Eastern Cooperative Oncology Group Performance Status; ES-SCLC=extensive-stage small-cell lung cancer; IV=intravenous; LDH=lactate dehydrogenase; PCI=prophylactic cranial irradiation; PD=progressive disease; Q3W=every 3 weeks; RECIST=Response Evaluation Criteria in Solid Tumors; SD=stable disease; ULN=upper limit of normal.

1.2.1 Treatment Assignment and Blinding

This is a randomized, open-label study. After written informed consent has been obtained, all screening procedures and assessments have been completed, and eligibility has been established for a participant, the study site will obtain the participants' study identification number from the interactive voice or Web-based response system (IxRS). For those participants who are eligible for randomization into the maintenance phase of the study, the study site will obtain the participant's randomization number and treatment assignment from the IxRS once eligibility has been established during the maintenance screening.

Participants will be randomly assigned to one of the two treatment arms: A) atezolizumab + lurbinectedin or B) atezolizumab. Randomization will occur in a 1:1 ratio through use of a permuted-block randomization method to ensure a balanced assignment to each treatment arm. Randomization will be stratified by:

- Eastern Cooperative Oncology Group Performance Status at maintenance baseline (0 vs. 1)
- Lactate dehydrogenase at maintenance baseline (\leq ULN vs $>$ ULN) via local laboratory test
- Presence of liver metastases at induction baseline (yes vs. no)
- Prior receipt of PCI (yes vs. no)

Although this is an open-label study, the randomized treatment assignments from the IxRS will be withheld from members of the Sponsor, including, but not limited to, the study's Medical Monitor, Study Statistician, Statistical Programmer, and Study Data Manager. Members of the Sponsor are not permitted to perform analyses or summaries by randomized treatment assignment and/or actual treatment received before the randomized treatment assignments are disclosed to the study team for the pre-specified analysis.

1.2.2 Independent Review Facility

An independent review facility (IRF) will perform a centralized, independent central review of images, and other clinical data as needed, prior to the efficacy analyses. IRF membership and procedures are detailed in an IRF charter.

1.2.3 Data Monitoring

An independent Data Monitoring Committee (iDMC) will evaluate safety data during the study. Sponsor affiliates will be excluded from iDMC membership. The iDMC will follow a charter that outlines the iDMC's roles and responsibilities.

Safety data will be reviewed on a periodic basis starting after approximately 24 participants have completed 2 cycles of maintenance treatment or 6 months from the time of the first participant randomized into the maintenance phase, whichever is earlier, and approximately every 6 months thereafter until the randomized treatment assignment

information is disclosed to the study team for the pre-specified analyses. All summaries and analyses for the iDMC review will be prepared by an independent Data Coordinating Center.

After reviewing the data, the iDMC will provide a recommendation to the Sponsor as described in the iDMC Charter. Final decisions will rest with the Sponsor.

Any outcomes of these data reviews that affect study conduct will be communicated in a timely manner to the investigators for notification of their respective Institutional Review Boards (IRBs)/ Ethics Committees (ECs).

2. STATISTICAL HYPOTHESES AND SAMPLE SIZE DETERMINATION

2.1 STATISTICAL HYPOTHESES

The purpose of this study is hypothesis testing and estimation regarding the effect of lorbunectedin in combination with atezolizumab on the duration of IRF-assessed progression-free survival (PFS) and/or OS compared with atezolizumab alone. The primary objective of this study is to evaluate the efficacy of lorbunectedin in combination with atezolizumab compared with atezolizumab. The primary endpoints for this study are OS and IRF-assessed PFS in the full analysis set (FAS).

The null and alternative hypotheses regarding IRF-assessed PFS or OS in the FAS can be phrased in terms of the survival function, the IRF-assessed PFS or OS survival functions $S_A(t)$ for lorbunectedin in combination with atezolizumab and $S_B(t)$ for atezolizumab.

$$H_0: S_A(t) = S_B(t) \text{ versus } H_1: S_A(t) \neq S_B(t)$$

2.2 SAMPLE SIZE DETERMINATION

Approximately 920 participants will be screened to achieve the enrollment of approximately 690 participants into the induction phase. Approximately █ participants will be randomized into this study for an estimated total of █ participants per treatment group.

2.2.1 Type I Error Control

[figure not shown]
The overall type I error (α) for this study is 0.05 (2-sided) and will be controlled for the primary endpoints of OS and IRF-assessed PFS according to RECIST v1.1 in the FAS with use of a group sequential weighted Holm procedure (Ye et al. 2013). A 2-sided $\alpha = 0.049$ and a 2-sided $\alpha = 0.001$ are allocated to OS and IRF-assessed PFS, respectively.

An alpha recycling from IRF-assessed PFS to OS will be conducted as follows: if the IRF-assessed PFS comparison is not statistically significant at a 2-sided $\alpha = 0.001$, the

primary comparison of OS will be tested at a 2-sided $\alpha=0.049$; if the IRF-assessed PFS comparison is statistically significant at the 2-sided $\alpha=0.001$, OS will be tested at a 2-sided $\alpha=0.05$. Additionally, if OS is statistically significant at the 2-sided $\alpha=0.049$, IRF-assessed PFS will be tested at a 2-sided $\alpha=0.05$.

The overview of the type I error rate control strategy is shown in [Figure 2](#) below.

Figure 2 Type 1 Error Rate Control Strategy

FAS = Full Analysis Set; IRF-assessed PFS=Independent Review Facility- assessed progression-free survival; OS=overall survival.

2.2.2 Overall Survival

The sample size determination is based on the number of events required to demonstrate efficacy with regard to OS in the FAS. The estimate of the number of events required is based on the following assumptions:

- 1:1 randomization ratio
- Two-sided significance level of 0.049 for the comparison of OS
- Approximately 85% power to detect an hazard ratio (HR)= 0.71 in OS, corresponding to an improvement in median OS from 12.5 months to 17.6 months in the FAS
- One planned interim analysis for OS at approximately 68% of the information fraction, with the stopping boundary determined by the Hwang-Shih-DeCani alpha spending function with the gamma parameter of -1.5 ([Hwang et al. 1990](#))
- Dropout rate of 5% over 24 months for each treatment arm for OS

With these assumptions, the final OS analysis will occur when approximately 323 deaths (72% of █ randomized participants) have been observed in the FAS. With these assumptions, the minimum detectable difference (MDD) in HR is approximately 0.793 for the final OS analysis. The final OS analysis is expected to occur approximately 41 months after the first patient is randomized.

2.2.3 IRF-assessed PFS

The primary IRF-assessed PFS analysis will be conducted at the time of the OS interim analysis when approximately 219 deaths in the FAS have been observed or when the minimum follow-up has been completed, whichever occurs later. The minimum follow-up is defined as 5 months after the target sample size of 450 participants has been randomized, or 5 months after the last participant has been randomized in case the final sample size is lower than 450 participants.

At the time of the OS interim analysis, it is estimated that approximately 392 IRF-assessed PFS events in the FAS will have occurred. This number of events provides more than 99% power to detect an HR= 0.5 in IRF-assessed PFS at a 2-sided significance level of 0.001, based on the following assumptions:

- 1:1 randomization ratio
- Median PFS of 2.6 months in the atezolizumab arm and 5.2 months in the atezolizumab + lorbinecetin arm (corresponding to a target HR=0.5)
- Dropout rate of 5% over 12 months for PFS
- No interim analysis for PFS

With these assumptions, the MDD in HR is approximately 0.72 for the IRF-assessed PFS analysis in the FAS.

3. ANALYSIS SETS

The participant analysis sets for the purposes of analyses are defined in [Table 3](#).

Table 3 Participant Analysis Sets

Participant Analysis Set	Description
FAS	All participants randomized into the maintenance phase regardless of whether or not the assigned study treatment is received: participants will be included in the analyses according to the treatment to which they were assigned by IxRS at randomization
SAS	All participants who are randomized into the maintenance phase and receive at least 1 dose of atezolizumab or lorbinecetin: participants will be analyzed according to the treatment that they received, i.e., participants who receive lorbinecetin in error will be analyzed in Arm A for the SAS
Enrolled analysis set	All participants who are enrolled in the induction phase, regardless of whether or not they receive induction treatment and regardless of whether they are subsequently randomized
Enrolled SAS	All enrolled participants, who receive at least 1 dose of atezolizumab or carboplatin or etoposide, regardless of whether or not they are subsequently randomized

FAS = full analysis set; IxRS=interactive voice/web-based response system; SAS = safety analysis set

4. STATISTICAL ANALYSES

4.1 GENERAL CONSIDERATIONS

Unless otherwise specified, all efficacy analyses will be performed in the FAS. Participants will be analyzed according to the treatment assigned at randomization by IxRS.

Unless otherwise specified, all safety analyses will be performed in the safety analysis set (SAS). Participants will be analyzed according to the treatment they actually received. Specifically, a participant will be included in the atezolizumab and lorbinecetin combination arm in the safety analyses if the participant receives any amount of lorbinecetin, regardless of the initial treatment assignment at randomization.

Unless otherwise specified, baseline measurements are the last available data obtained prior to the participant receiving the first dose of any component of protocol treatment in the maintenance phase.

4.2 PRIMARY ESTIMANDS ANALYSIS

4.2.1 Definition of Primary Estimands

The primary objective for this study is to evaluate the efficacy of lorbinecetin when administered in combination with atezolizumab compared with atezolizumab monotherapy in participants with ES-SCLC, who have an ongoing response or SD after completion of 4 cycles of carboplatin, etoposide, and atezolizumab induction treatment on the basis of primary endpoints: IRF-assessed PFS according to RECIST v1.1 and OS, as defined in Section 1.1 (see [Table 1](#)) in estimands framework.

4.2.2 Main Analytical Approach for Primary Estimands

For IRF-assessed PFS, participants who have not experienced disease progression and have not died by the clinical cutoff date will be censored at the time of the last tumor assessment. Participants who have no tumor assessment after baseline and have not died by the clinical cutoff date will be censored at the date of randomization.

For OS, participants who are not reported as having died by the clinical cutoff date will be censored at the date when they were last known to be alive. Participants who do not have information after baseline will be censored at the date of randomization.

Participants who are lost to follow-up will be censored at the last date they were known to be alive for the primary analysis of OS.

Each of the primary endpoints will be compared between two treatment arms based on the stratified log-rank test. The HR will be estimated with use of a stratified Cox regression model, including two-sided 95% confidence intervals (CIs). The stratification factors will be those used for randomization (as listed in Section 1.2.1). The Kaplan-Meier methodology will be used to estimate the median IRF-assessed PFS and median OS for each treatment arm, and Kaplan-Meier curves will be constructed to provide a

visual description of the difference between treatment arms. The Brookmeyer-Crowley methodology will be used to construct the 95% CIs for the median IRF-assessed PFS and median OS for each treatment arm ([Brookmeyer and Crowley 1982](#)). Results from an unstratified analysis will also be provided.

4.2.3 Sensitivity Analyses

If >5% of participants are lost to follow-up for OS in either treatment arm, a sensitivity analysis will be performed for the comparisons between two treatment arms in which participants who are lost to follow-up will be considered as having died at the last date they were known to be alive.

The impact of missing scheduled tumor assessments on IRF-assessed PFS will be assessed depending on the number of participants who missed tumor assessments scheduled immediately prior to the date of disease progression per RECIST v1.1 or the data cutoff. If >5% of participants missed two or more consecutive assessments scheduled immediately prior to the date of disease progression per RECIST v1.1 or the data cutoff in any treatment arm, the following sensitivity analysis will be performed:

- Participants who missed two or more consecutive scheduled assessments immediately prior to the date of disease progression per RECIST v1.1 or death will be censored at the last tumor assessment prior to the missed visit.

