	
 • Variable: IRF-assessed progression-free survival (PFS) after randomization, defined as the time from randomization to the first occurrence of disease progression (as determined by IRF according to RECIST v1.1) or death, whichever occurs first • Treatment: 
 – Experimental arm: atezolizumab 1200mg IV + lurbinectedin 3.2mg/m² IV on Day 1 of each 21-day cycle – Control arm: atezolizumab 1200 mg IV on Day 1 of each 21-day cycle • Intercurrent events and handling strategies: 
 – Early discontinuation from study treatment for any reason: treatment policy strategy – Start of non-protocol anti-cancer therapy prior to the respective event of interest: treatment policy strategy • Population-level summary: hazard ratio (HR) for IRF-assessed PFS

 • To evaluate the efficacy of lurbinectedin in combination with atezolizumab compared with atezolizumab 	
 • Population: as defined above • Variable: Overall survival (OS) after randomization, defined as the time from randomization to death from any cause • Treatment: as defined above • Intercurrent events and handling strategies: as defined above • Population-level summary: HR for OS

ES-SCLC=extensive-stage small-cell lung cancer; CR=complete response; HR=hazard ratio; IRF = independent review facility; IV=intravenous; OS = overall survival; PFS = progression-free survival; PR=partial response; RECIST = response evaluation criteria in solid tumors; SD=stable disease.

Table 2 Secondary and Exploratory Objectives and Endpoints for Randomized Participants

Secondary Objectives	Corresponding Endpoints

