4.2.4 Supplementary Analyses

The following supplementary analyses will be performed for the primary efficacy endpoints of OS and IRF-assessed PFS in which a different handling rule of intercurrent events is implemented to provide further understanding of the treatment effect.

To assess the impact of the intercurrent event of starting a non-protocol anti-cancer therapy (NPT) prior to a PFS event, the primary analysis of IRF-assessed PFS will be repeated with such intercurrent event handled using a hypothetical strategy, if >5% of participants received NPT prior to a PFS event in either treatment arm. To estimate the estimand that implements this strategy, participants who start an NPT before a PFS event will be censored at the time of the last tumor assessment before the initiation of NPT.

To assess the impact of the intercurrent event of starting an NPT on OS, the primary analysis of OS will be repeated with such intercurrent event handled using a hypothetical strategy if >10% of participants received NPT in either treatment arm. The discounted method uses a “discounted” survival time after NPT usage for patients who received NPT based on a user-specified assumption for the effect in OS. The duration from initiation of NPT to death or censoring date may be discounted according to a range of possible effects on OS of the subsequent NPT (e.g., 10%, 20%, 30%, etc). After adjustments are made for the effect of subsequent NPT on OS, the methods that are outlined for OS in Section [4.2.2](#) will be used for these analyses.

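### The >5% trigger for the missed-scan sensitivity analysis of IRF-assessed PFS leaves out deaths after missed scans, although the analysis re-censors those deaths

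*SAP*

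**What the plan says.** SAP 4.2.3 plans one sensitivity analysis for missed tumour assessments and makes it conditional.

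- **Lead-in:** the assessment depends on "the number of participants who missed tumor assessments scheduled immediately prior to the date of disease progression per RECIST v1.1 or the data cutoff".
- **Trigger:** the analysis is performed if more than 5% of participants in any arm "missed two or more consecutive assessments scheduled immediately prior to the date of disease progression per RECIST v1.1 or the data cutoff".
- **Rule:** anyone having "missed two or more consecutive scheduled assessments immediately prior to the date of disease progression per RECIST v1.1 or death will be censored", with the date set back to the final scan ahead of the gap.

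SAP Table 1 (Section 1.1) defines PFS as running from randomization "to the first occurrence of disease progression (as determined by IRF according to RECIST v1.1) or death, whichever occurs first". Under SAP 4.2.2, participants without progression who "have not died by the clinical cutoff date will be censored at the time of the last tumor assessment".

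Protocol 9.4.2.1 leaves sensitivity analyses to the SAP, and SAP Section 5 lists no supporting document. No other text reconciles the trigger with the rule.

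**The concern.** Call two or more consecutive missed scheduled scans a gap. The trigger counts gaps before progression or the data cutoff. The rule acts on gaps before progression or death. Death is in the action but missing from both trigger sentences.

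A death without earlier IRF progression is a primary PFS event, dated at death. With scans every 6 weeks to week 48 (Protocol 8.1.1), two missed scans span about 12 weeks, or 2.8 months. That is longer than the 2.6-month control median PFS assumed in SAP 2.2.3, so progression may have come well before the recorded event. These are the events the sensitivity analysis is meant to probe, yet they do not help to set it off.

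The trial is open-label, and Protocol 4.2 cites predefined missing-data and censoring rules among its safeguards. This is the only missed-scan analysis planned for a primary endpoint, and it could be skipped although one arm has many deaths after gaps.

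**Working it through.** **1. The plan's own PFS figures.** Inputs from SAP 2.2.3: 392 events, HR 0.5, two-sided alpha 0.001, 1:1 allocation.

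- Power = Φ(√392 × |ln 0.5| / 2 − 3.2905) = Φ(6.862 − 3.291) = 0.9998; the SAP states more than 99%.
- Minimum detectable HR = exp(−2 × 3.2905 / √392) = 0.717; the SAP states 0.72.

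Both reproduce. If the rule removed 12 to 60 events, 380 to 332 would remain. Power at HR 0.5 would still exceed 99.8%, and the minimum detectable HR would be 0.713 to 0.697. Power is not at issue.

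**2. Who is counted and who is re-censored.**

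| Gap immediately before | Counted by trigger | Changed by rule |
|---|---|---|
| Progression | yes | yes |
| Death | no | yes |
| Data cutoff, alive and event-free | yes | no, already censored at last scan (SAP 4.2.2) |

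The neighbouring conditional analyses do match. For OS in SAP 4.2.3, the participants counted as lost to follow-up are those the rule treats as dead. For new anti-cancer therapy in SAP 4.2.4, the trigger is "if >5% of participants received NPT prior to a PFS event in either treatment arm" and the rule is that "participants who start an NPT before a PFS event will be censored at the time of the last tumor assessment".

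**3. The threshold.** The target of 450 (SAP 2.2.3) split evenly gives 225 per arm. 0.05 × 225 = 11.25, so 12 participants are needed (11/225 = 4.9%, 12/225 = 5.3%).

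- 12, 20 or 30 gap-deaths in an arm (5.3%, 8.9%, 13.3%) add 0 to the count as written. Each would trigger the analysis if deaths counted.
- 11 progression or cutoff gaps plus 5 gap-deaths: 11/225 = 4.9% as written, not run; 16/225 = 7.1% with deaths, run.

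**4. How many gap-deaths there might be.** The documents do not say. Assume 196 events per arm (392/2), 5-30% of them deaths without IRF progression, and 20-60% of those after a gap. The low end is 196 × 0.05 × 0.2 ≈ 2 per arm and the high end 196 × 0.30 × 0.6 ≈ 35, or 0.9% to 15.7% of 225. The uncounted group alone can lie on either side of 5%.

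**5. Effect on the hazard ratio (illustrative simulation).** From the documents: PFS medians 2.6 and 5.2 months, the scan schedule, and dropout of 5% over 12 months. Assumed: 225 per arm and uniform accrual over 18, 23 or 28 months with cutoff 5 months later, giving 379-404 events against the planned 392. There were 300 runs per setting. Results for 23 gap-deaths (10%) per affected arm at 23-month accrual (percentages can differ in the last digit from ratios of the rounded HRs):

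| Affected arm | Progression dated at the scan | Continuous progression times |
|---|---|---|
| Experimental only | 0.508 to 0.472 (−7.0%) | 0.502 to 0.476 (−5.2%) |
| Control only | 0.487 to 0.509 (+4.4%) | 0.501 to 0.513 (+2.2%) |
| Both | 0.503 to 0.490 (−2.6%) | 0.504 to 0.489 (−2.9%) |

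- Across all accrual settings: 23 in one arm 2.1-7.3%; 12 in one arm 1.0-3.7%; 23 in both arms 2.4-3.1%. Log-rank p stayed below 0.001 in at least 99.7% of runs, before and after the rule.
- Deaths following a progression that no scan recorded (assumed median 3 or 6 months from progression to death, 150 runs): up to 8.1% in one arm and 9.6% in both.
- True HR 0.72 (23-month accrual, 250 runs): 23 in one arm 1.6-4.8%; 12 in one arm 0.7-2.5%.

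**6. Could cutoff gaps from planned dropout fire the trigger anyway?** Counting every dropout gives about 3.1-4.1 control and 4.9-6.3 experimental participants, with at most about a 4% chance of reaching 12. These are upper bounds, because scheduled scans also end at withdrawal of consent (Protocol 8.1.1).

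**The case against.** **Another reading exists.** Scheduled scans end at death, so for someone who died without progression the last scans due before the cutoff are the pre-death ones. On that view, progression and cutoff together cover everyone. The reading is strained: the rule names death separately, and SAP 4.2.2 distinguishes participants who have not died by the cutoff. It supports calling this a drafting slip, not leaving the text as it is.

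**The trigger sets when the analysis is mandatory and does not forbid running it otherwise.** True, but an analysis run outside its stated condition loses the standing of a prespecified one.

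**Poor attendance that produces gap-deaths also produces cutoff gaps, which do count.** This is the strongest point. About 219 deaths are expected at this analysis (219/450 = 49%), so roughly half of participants would be alive. In simulations with scanning stopping at a constant rate (assumed, 23-month accrual), a median of 10 months from stopping scans to death gave about 22-23 gap-deaths alongside 21-23 cutoff gaps. The existing trigger then fired in at least 98% of runs with 12 or more gap-deaths. At 6 months it fired in about 55-80% of such runs, with about 26 gap-deaths per arm. At 3 months, about 13-36 control gap-deaths came with only 3-7 cutoff gaps, and it fired in 0-4% of control-arm runs with 12 or more gap-deaths. A wrongly skipped analysis is therefore a risk mainly when participants who stop attending die soon afterwards. The control medians in the SAP (PFS 2.6, OS 12.5 months) suggest longer survival after progression on average, but patients who stop scanning because they are deteriorating may be a worse-than-average group.

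**The practical consequence is small.** This stands. The gap counts are assumptions, Protocol 8.1.1.1 requires scans to continue after treatment stops and after new therapy starts, and the SAP 4.2.4 analysis of new therapy covers some of the same participants.

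**Conclusion.** The concern holds and is minor. Both trigger sentences omit a type of event that the rule re-censors, and nothing elsewhere repairs it. Read plainly, the analysis is not required, whatever the number of gap-deaths, provided neither arm reaches 12 progression and cutoff gaps combined.

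Confidence in the mismatch is high. Whether it would change the decision to run the analysis cannot be known from the documents, because they report no gap counts. The simulated HR shifts rest on assumed accrual, assumed gap counts and, for the largest values, an assumed time from unrecorded progression to death.

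The reverse mismatch, cutoff gaps that count but are not altered, does no harm: at worst it prompts a run that changes nothing for those participants.

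**What to change.** Add death, alongside progression and the data cutoff, to the lead-in and to the threshold sentence of SAP 4.2.3, so that the trigger covers everyone the rule re-censors. Keeping the cutoff is harmless; triggering on progression or death alone, or running the analysis unconditionally, would also resolve the mismatch. Report the number of participants with gaps by arm and by type (progression, death, cutoff).

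Timing matters. SAP 2.2.3 states: "The primary IRF-assessed PFS analysis will be conducted at the time of the OS interim analysis". The Version 8 rationale in the protocol says the cutoff for the final OS analysis has been reached, so PFS has probably been analysed. In that case, present the gap counts and the corrected analysis as post hoc.

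The cost is one phrase in two sentences or, after the fact, one count table and one rerun of the PFS program on existing data.
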